4 PATIENT SELECTION

Written informed consent must be obtained before any study specific procedures are performed.

4.1 Eligibility criteria for entry into the main study

The Investigator will determine patient eligibility based on the following inclusion/exclusion criteria.

4.1.1 Inclusion criteria:

Patients will only be eligible for inclusion in this study if all of the following criteria apply:

1. Pathologically confirmed advanced solid tumour with liver metastasis suitable for intervention (as assessed by ultrasound or other radiological methods). In addition confirmed primary liver tumours (hepatocellular carcinoma or cholangiocarcinoma) can be included.
2. Will have progressed or remained stable on conventional chemotherapy.
3. Male or Female, Age ≥ 18 years.
4. Have life expectancy of ≥ 3 months.
5. Left Ventricular Ejection Fraction (LVEF) $\geq 50\%$ on echocardiogram.
6. Have not received radiotherapy to the target area within the preceding 12 months.
7. A World Health Organisation (WHO) performance status of ≤ 1 (Appendix 1).
8. Able and willing to give written informed consent, indicating that they are aware of the investigational nature of this study and potential risks, and able to comply with the protocol for the duration of the study, including scheduled follow-up visits and examinations.

4.1.2 Exclusion criteria:

Patients will be ineligible for recruitment to the study if any of the following conditions hold:

1. Have surgery or other procedure requiring general anaesthesia planned to be undertaken during the period of the study.
2. Have serious illnesses including, but not limited to, congestive heart failure (NYHA class III or IV functional classification); life threatening cardiac arrhythmia; or myocardial infarction or cerebral vascular accident within the last 6 months.
3. Have on going significant infection (chest, urine, blood, intra-abdominal).
4. Have uncontrolled diabetes.
5. Have received a life-time dose of doxorubicin $> 450 \text{ mg/m}^2$ or a life-time dose of epirubicin $> 900 \text{ mg/m}^2$ or any dose of both.
6. Pregnant or breast-feeding. In women of childbearing potential, a negative pregnancy test (serum) is required within 30 days prior to study intervention.
7. Female participants of child bearing potential and male participants whose partner is of child bearing potential who are not willing to practice an acceptable form of contraception (i.e. oral contraceptive, diaphragm, cervical cap, condom, surgical sterility) during the study and for 6 months thereafter. Women whose partner has or men who have undergone a vasectomy must use a second form of birth control.
8. Have any known allergic reactions to any of the drugs or liposomal components or intravenous imaging agents to be used in this study.
9. Have portal or hepatic vein tumour invasion/thrombosis.
10. Inadequate Haematological and Biochemical indices:

Lab Test	Exclude if:
INR	> 1.5 times the institution's upper normal limit (UNL)*
Absolute neutrophil count	$< 1,500/\text{mm}^3$ (or $< 1.5 (10^9/\text{L})$)
Platelet count	$< 60,000/\text{mm}^3$ (or $< 60 (10^9/\text{L})$)
Hgb	$< 9.0 \text{ g/dL}^{**}$
Serum creatinine, or Calculated creatinine clearance (CrCl)	$\geq 2.5 \text{ mg/dL}$ (or $\geq 221 \mu\text{mol/L}$) $\leq 25.0 \text{ mL/min.}$
Serum bilirubin	$> 3.0 \text{ mg/dL}$ (or $> 51 \mu\text{mol/L}$)

Serum albumin	< 2.8 g/dL (or <28 g/L)
---------------	-------------------------

* Except in patients who are therapeutically anticoagulated for medical conditions unrelated to cancer such as atrial fibrillation. Subjects may be re-screened after the condition is treated or anticoagulant is withheld

** Unless the haemoglobin value has been stable, the patient is cardiovascularly stable, asymptomatic, and judged to withstand the FUS procedure

11. Have contraindications to receiving doxorubicin including prior sensitivity (rash, dyspnoea, wheezing, urticarial or other symptoms) attributed to anthracyclines or other liposomal drugs.
12. Use of chemotherapy or of an investigational drug within 30 days or 5 half-lives, whichever is longer, preceding the intervention.
13. Have medically significant active infection.
14. Have Child-Pugh Class C liver disease, or Class A-B with encephalopathy and/or refractory ascites (Appendix 3).
15. Documented HIV positive.
16. Documented diagnosis of haemochromatosis.
17. Documented history of contrast-induced nephropathy.
18. Have any of the following contraindications for liver biopsy:
 - a. Suspected liver haemangioma or other vascular tumour
 - b. Tense ascites
 - c. Known cystic liver disease*
 - d. Extra-hepatic biliary obstruction*

(* Relative contraindications only and may be non-exclusive at discretion of the study team)
19. Other medical or psychiatric conditions or laboratory abnormalities that the investigator considers would make the patient a poor trial candidate.

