³ Best efforts will be made to ensure all screening procedures & required tests occur during a single screening visit but, but according to resources and patient preference, one or more additional screening visit(s) may occasionally be required.

⁴ It is not compulsory for participants to be admitted on day -1. I.e. the patient can attend to complete pre-intervention assessments and return on day 1 to be admitted for the intervention.

⁵ Echocardiogram will only be repeated if clinically indicated.

WHO PS				X							
Haematology tests ⁶				X				X	X	X	
Biochemistry tests ⁷				X				X	X	X	
Group & Save ⁸				X							
Coagulation studies ⁹				X							
Pre-operative Anaesthetic Assessment (ASA Classification)				X							
Ultrasound Session ¹⁰		X		X							
Liver MRI/MR Spectroscopy ¹¹					X			X ¹²		X	X
Liver pCT ¹³					X					X	X
Whole Body FDG PET-CT					X					X	X
Pre-medication						X					
FUS + ThermoDox®							X				
ThermoDox® Plasma Samples							X ¹⁴				
Tumour Biopsy Samples							X ¹⁵				
Adverse Event Review							X	X	X	X	

* The 4 week follow-up visit will mark the end of the study and the participant will be free to consider other studies from this point, however scans may be performed after this time point in the flexible scan follow-up visit if that participant is not already enrolled on another study at that time.

** The flexible radiology follow-up visit will be chosen based on patient preference, available imaging slots and emerging radiological data. Patient visits will be minimised where possible. The flexible scan visit will be performed at least a week either side the 4 week follow-up visit, and may coincide with the 2 week follow-up visit.

In Part II, the number of follow-up MRI/MR-Spectroscopy, Liver pCT and whole body FDG PET-CT scans may be reduced, if the data from Part I informs that a more efficient (in terms of reducing patients & site requirements) schedule is possible.

⁶ Full Blood Count (FBC); including Haemoglobin (Hb), white blood cells (WBC) with differential count (neutrophils and lymphocytes) and platelets.

⁷ Biochemical profile to include U&Es, (Na⁺, K⁺, Ur, Cr), phosphate, calcium, LFTs (total protein, ALP, Albumin, ALT or AST, Bili, LDH) (validity period for bloods is 3 days).

⁸ Group & Save, as standard for surgical candidates, date of valid test to be recorded on CRF, not blood group. Can alternatively be performed on d-1.

⁹ Coagulation studies are performed at baseline only (PT & APTT).

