4.3 Re-screening if patient does not meet inclusion/exclusion criteria first time round

If a patient does not meet the inclusion/exclusion criteria first time round, he/she can be re-screened. Patients who fail at re-screening are ineligible for the TARDOX study and may not be re-screened again.

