APPENDIX 3: CHILD-PUGH SCORE

The Child-Pugh Score [49, 50] is used to assess chronic liver disease. It is calculated by adding the points for the five criteria assessed:

Points	1	2	3
Encephalopathy	None	Minimal	Advanced (coma)
Ascites	Absent	Controlled	Refractory
Bilirubin ($\mu\text{mol/L}$) (mg/dl)	<34 <2	34-50 2-3	>50 >3
Albumin (g/dL)	>3.5	2.8-3.5	<2.8
INR	<1.7	1.71-2.30	>2.30

The Child-Pugh Score is interpreted as follows:

Points	Class	One year survival	Two year survival
5-6	A	100%	85%
7-9	B	81%	57%
10-15	C	45%	35%

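### The INR exemption for anticoagulated patients (4.1.2, item 10, footnote *) carries no ceiling, hold or repeat test before a planned liver biopsy, and it is unclear whether the re-screening sentence covers them

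*Protocol*

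**What the plan says.** The laboratory table in Protocol 4.1.2, item 10, excludes an INR above 1.5 times the institution's upper normal limit (UNL). Footnote * to that row has two sentences. The first is an exemption: "Except in patients who are therapeutically anticoagulated for medical conditions unrelated to cancer such as atrial fibrillation". The second concerns re-screening: "Subjects may be re-screened after the condition is treated or anticoagulant is withheld".

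Footnote ** in the same table exempts some patients from the haemoglobin limit, but attaches conditions: "Unless the haemoglobin value has been stable, the patient is cardiovascularly stable, asymptomatic, and judged to withstand the FUS procedure".

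Section 4.3 gives the general rule on re-screening: "If a patient does not meet the inclusion/exclusion criteria first time round, he/she can be re-screened". A patient who fails the second time may not be screened again.

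On testing, footnote 9 to the Summary of Schedule Events reads "Coagulation studies are performed at baseline only (PT & APTT". Screening runs from Day -30 to Day -2 (5.1). The lists for Day -1, Day 1 and Day 2 in 5.2 contain no clotting test.

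On biopsy, Part I takes three samples through one co-axial needle (Synopsis) and Part II up to two (5.4.2).

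**The concern.** The INR limit is the only coagulation value that the protocol requires before it puts a needle into a liver tumour. For one foreseeable group, of which the footnote itself gives atrial fibrillation as an example, the limit is removed and nothing replaces it. Taken at its word, the first sentence lets such a patient go on to biopsy at any INR, with no required hold and no scheduled test near the procedure.

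The second sentence suggests that something else may have been meant, namely withholding the drug and testing again. It does not say so, and it does not identify its subjects. Two investigators could reasonably handle the same patient differently.

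The harm at stake is bleeding after biopsy. These biopsies are taken to supply the primary endpoint, so the protocol itself creates the exposure.

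**Working it through.** The plan states no figure here to reproduce. The check sets the provisions side by side, with a little arithmetic for scale.

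**1. Whom the exemption affects.** It matters only above 1.5 × UNL. The protocol gives no UNL. If it is assumed to lie between 1.0 and 1.3, the limit lies between 1.5 × 1.0 = 1.5 and 1.5 × 1.3 = 1.95. Above that value an exempt patient has no stated upper bound.

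**2. Two readings of the re-screening sentence.**
- *Reading A: it refers to the exempt patients.* The mention of a condition and an anticoagulant points back to the first sentence. But 4.3 offers re-screening to patients who have failed a criterion, and an exempt patient has not failed on INR. On this reading the footnote intends hold-and-retest without saying so, and the patient uses up the single re-screen allowed.
- *Reading B: it refers to subjects who exceed the limit and are not exempt,* for example those anticoagulated for a cancer-related reason or with another treatable cause of a raised INR. The two sentences are then compatible, and the exempt patient enters directly with no INR condition at all.

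The text does not settle the choice. Reading A leaves the intended rule unwritten; Reading B makes the waiver fully unconditional. The footnote needs correcting in both cases.

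**3. Whether another provision supplies an INR condition.**

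| Provision | Bears on bleeding risk? | Sets an INR value? |
|---|---|---|
| Item 10, platelet limit | Yes, no exemption | No |
| Item 18, liver-biopsy contraindications | Yes | No coagulation entry |
| Item 19, investigator's judgement | Yes | No |
| 4.2 and 4.4, consult the trial office or Chief Investigator when unsure | Indirectly | No |
| 5.1.3, anaesthetic pre-assessment | Yes | No |
| 5.4.2, plugging of the needle track | Yes | No |
| 13.4, biopsy according to current guidelines | Yes | None stated |

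**4. Age of the only scheduled clotting result on Day 1.** There is no Day 0. From Day -30 to Day 1 is 30 days, and from Day -2 to Day 1 is 2 days, so the result is 2 to 30 days old. Schedule footnote 7, attached to biochemistry, adds "validity period for bloods is 3 days". If that also covers coagulation, the result is at most 3 days old. Even then, an exempt patient has no value to meet.

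**5. Background risk in the protocol's own source.** Table 9 (13.4) reproduces a national liver-biopsy audit: haemorrhage in 14/3476 = 0.40% and death in 4/3486 = 0.11%. The text attributes all four deaths to bleeding. These rates describe liver biopsy in general. They are not rates for anticoagulated patients, and the protocol provides none.

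**The case against.** The strongest reply is that eligibility is not clearance for biopsy. Exempting someone from an entry limit does not tell anyone to biopsy at that INR. A radiologist takes the sample, the protocol refers to current guidelines, the anaesthetic clinic reviews the results before the patient proceeds, and item 19 lets the investigator exclude on a laboratory abnormality. This is a single-site trial, and 4.2 and 4.4 direct a doubtful investigator to the trial office or the Chief Investigator. All of this stands as mitigation and lowers the chance of harm. None of it sets an INR condition, however, and an investigator who reads an explicit exemption literally has no reason to feel doubt.

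A reader might also infer that the footnote contradicts itself, by admitting these patients in one sentence and requiring the drug to be withheld first in the next. The document does not support that. The second sentence is permissive, contains no word such as *only*, allows treatment of the condition as an alternative to withholding the drug, and is consistent with the first sentence under Reading B.

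Finally, the sponsor may have meant the exemption as it stands. That is possible. If so, the absence of a ceiling is the whole problem, and footnote ** shows that conditions can be written into an exemption in this very table.

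**Conclusion.** The point holds as an ambiguous, unconditional exemption and should be fixed. The protocol removes its only INR condition for a foreseeable group before a planned liver biopsy, puts nothing in its place, and leaves open whether the re-screening sentence was meant to do so.

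The effect is confined to participant safety. The number of affected patients among the maximum of 28 evaluable participants is unknown and may be zero, and the documents do not allow the excess bleeding risk to be estimated. The primary endpoint, sample size and analysis are untouched.

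The conclusion rests on the protocol text alone. A pharmacy, radiology or departmental procedure outside it may already impose an INR limit at biopsy; if so, the correction merely writes existing practice into the protocol. The INR range of 1.5 to 1.95 depends on the assumed UNL, but the finding does not.

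**What to change.** Reword footnote * along these lines: *A patient whose INR is raised by therapeutic anticoagulation may be enrolled only if the anticoagulant can safely be withheld or managed so that a repeat INR, taken on Day -1 or Day 1 before anaesthesia and before the ThermoDox infusion, is no more than 1.5 × UNL. Other subjects with a treatable cause of a raised INR may be re-screened once it has been treated.* Add the repeat test, for these participants only, to schedule footnote 9 and to the Day -1/Day 1 lists in 5.2.

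The timing matters. In Part II the co-axial needle can go in after FUS exposure (5.4.2), and so after the infusion. A check tied to needle insertion could then fail a patient who has already been anaesthetised and dosed and who could not be biopsied. Testing before anaesthesia and infusion avoids this in both Parts.

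The rewording narrows the present exemption and drops its distinction between cancer-related and other anticoagulation. If the sponsor does want biopsies under continued anticoagulation, the footnote should say so and name the highest acceptable INR.

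The cost is one criterion footnote, one schedule footnote and an entry in 5.2; the synopsis only refers to 4.1.2 and can stay. A few participants need one more routine blood test, and a patient whose anticoagulant cannot safely be withheld may be lost.

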4.2 Protocol deviations and waivers to entry criteria

Protocol adherence is a fundamental part of the conduct of a clinical study. Changes to the approved protocol need prior approval unless for urgent safety reasons.

Investigators must contact the TARDOX Trial Office to obtain guidance and/or clarification as necessary if unsure whether the patient satisfies all the entry criteria and to clarify matters of clinical discretion. The trial office will contact the chief investigator or clinical coordinators as necessary. Requests for protocol waivers to enter a patient that is clearly ineligible will not be granted.

Investigators should not deviate from the protocol for the management of enrolled subjects deliberately unless essential to protect the rights or safety of the individual. Examples might include the addition or deletion of tests, dosing, duration of treatment etc. It may be necessary to withdraw the patient from further study. All deviations should be fully documented/ justified and reported to the trial office without delay. Deviations should be discussed with the trial office and/or the Chief Investigator prior to being actioned where possible.

4.3 Re-screening if patient does not meet inclusion/exclusion criteria first time round

If a patient does not meet the inclusion/exclusion criteria first time round, he/she can be re-screened. Patients who fail at re-screening are ineligible for the TARDOX study and may not be re-screened again.

4.4 Patient registration procedure

Participants will be recruited from patients referred to oncology services for the management of metastatic cancer from solid tumour primaries. A screening log must be kept of all patients considered for the study including any that are subsequently excluded; the reason for exclusion must be recorded on this form. A copy of the screening log should be sent to the trial office on request, but without patient identifiers. The original must be retained on site. Before entering a patient onto the study the Principal Investigator or designee will confirm eligibility. If in any doubt the Chief Investigator must be consulted before entering the patient.

A completed patient registration / eligibility checklist along must be sent to the TARDOX Trial Office. Each patient must be registered with the TARDOX Trial Office using this Registration Form and receive a unique trial number by the TARDOX Trial Team.

Patients should be registered by the site by faxing the registration form to the TARDOX Trial Office using [contact]**. Alternatively the scanned Registration Form can be emailed to: [contact]. The Fax/Email service is available 24 hours a day (Faxes/emails received outside office hours, 09:00 – 17:00 Monday to Friday, will be dealt with the next working day). Registration Forms will be provided in the Investigator Site File. Following registration, the site will be notified by fax or email that a patient has been successfully entered into the trial and of the patient's unique trial number.

The original Registration Form should be passed to the TARDOX Trial Office once complete.

5 TRIAL ASSESSMENTS AND PROCEDURES

Please refer to the Summary Schedule of Events given at the front of this protocol. Details of all protocol evaluations and investigations must be recorded in the patient's medical record for extraction onto the CRF.

5.1 Screening (d-30 to d-2)

The following must be performed within days -30 to -2, where day -1 is the day of admission for intervention. The exception is the Ultrasound Session (section 5.1.3.1) which can take place as early as day -40 if separate consent is obtained. Tests performed as part of routine standard of care need only be repeated if outside the time window.

Consenting patients will be enrolled into the study once all eligibility has been confirmed. In the patient's interests, best efforts will be made to ensure that consent and screening procedures are performed in the least number of visits possible (sections 5.1.2 and 5.1.3).

5.1.1 Optional Two Stage Screening

Informed consent by patients to screen for the trial may be sought in one process using the main Consent Form (CF) and the main PIS*. Or, optionally, informed consent can be separated into two stages; ultrasound screening followed by, if suitable, informed consent for the full study and remaining screening assessments.

The two stage process allows the ultrasound screening session to be performed and the feasibility of intervention decided in advance of commencing other screening assessments. This can avoid the patient having to complete informed consent for the full study and potentially undergoing other screening tests before ultrasound screening. A separate Ultrasound Screening CF and Patient Information Sheet (PIS) are available for this purpose. Potential participants who consent for ultrasound screening who are successfully screened will then be provided with the main PIS and, after informed consent, be offered to complete consent for the other screening assessments. If eligible the patient can then be enrolled on the study.

**The main PIS and main CF encompasses the ultrasound session screening assessment, therefore it is not necessary to complete the separate ultrasound screening CF and PIS if the one stage process is planned and the patient has provided informed consent on the main CF.*

5.1.2 Informed Consent

Potential participants will be given a current, approved version of the PIS. They will also receive clear verbal information about the study detailing no less than: the nature of the study; the implications and constraints of the protocol; the known side effects and any risks involved in taking part. It will be explained that they will be free to withdraw from the study at any time, for any reason, without prejudice to future care, and with no obligation to give a reason for withdrawal. They will have at least 24 hours to consider the information provided and the opportunity to question the Investigator, their GP or other independent parties before deciding whether to participate. The patient must personally sign and date the latest approved version of the relevant CF before any study procedures are performed, outside of standard care.

The Investigator (or delegate) who obtains consent must be suitably qualified and experienced. All delegates working on behalf of the investigator must be authorised by the PI. The Investigator is responsible for ensuring that the trial consent procedures comply with current applicable GCP Regulatory and ethical requirements. Informed consent discussions and outcomes must be well documented in the medical record. The Investigator (or delegate) must be satisfied that the patient has made an informed decision before taking consent. The patient and the Investigator (or delegate) must personally sign and date the current approved version of the informed consent form in each other's presence. A copy of the information and signed consent form will be given to the participant. The original signed form will be retained in the medical record and a copy is to be filed in the Investigator Site File.

Contraceptive/ Pregnancy counselling

Doxorubicin, the active chemotherapy agent of the study drug (ThermoDox®) can cause foetal harm when administered to a pregnant woman. Animal studies have demonstrated teratogenic and embryotoxic effects at low doses. There are no adequate and well-controlled studies in pregnant women.

All participants must be advised on the need to use reliable methods of contraception during the study and for six months after intervention. The advice should include:

- (1) The acceptable methods, including: male or female sterilization, implants, injectables, combined oral contraceptives, some intrauterine devices (IUDs), and abstinence.
- (2) The recommendation that a barrier method should be used in addition to another form of contraception.
- (3) Males should continue to take these precautions for a minimum six months after the intervention.
- (4) Females should continue to take these precautions a minimum of six months after the intervention.
- (5) That any pregnancy (also applies to females partners of male trial subjects) occurring within six months of the trial intervention will be followed up and the outcome of all pregnancies (spontaneous miscarriage, elective termination, normal birth or congenital abnormality) will be reported and followed up even if participant is discontinued from the study.

Breast-feeding counselling

There is the potential for serious adverse effects in breast-feeding infants from doxorubicin administered to nursing mothers and consequentially, breast-feeding women are excluded from this study (see exclusion criteria).

